### **B. Analysis Plan**

#### *1. Primary and Secondary Outcomes*

Behavioral data analysis (food intake + hedonic ratings of food). Continuous variables will be summarized by descriptive statistics (e.g., mean, SD, range, median), examined via graphical analyses (e.g. histogram, Q-Q plot) and analyzed to assess the normality of the data. Data transformation of continuous variables will be used as necessary. Model assumptions and potential outliers will be analyzed with various modeling diagnostics and plotting techniques. Visual analog scale (VAS) measures will be analyzed using PROC MIXED implemented in SAS (Version 9.4, Cary, NC). VAS scales for milkshake, snack food pleasure and desire, ad lib intake of those foods as well as changes in hunger (fasted to fed) will be entered into 2x2 repeated measures mixed models including drug-by-gene interactions which addresses Aim 1a and Aim 2. Control variables of no interest to be included are BMI, gender, visit number and nausea (after scan assessments only). In addition to main effects of the drug and the TaqIA allele status, interactions with  $p < 0.10$  will be probed with least squared mean comparisons of a priori contrasts of interest including tests of the: 1) impact of TaqIA allele status with bromocriptine, 2) impact of TaqIA allele status without bromocriptine 3) impact of bromocriptine on those with the TaqIA A2/A2 variant, and 4) impact of bromocriptine on those with at least one TaqIA A1 variant.

fMRI data preprocessing: Neuroimaging data will be preprocessed using the fMRIPrep pipeline [45]. DICOMS will be converted to the Brain Imaging Data Structure (BIDS file structure) [46], then preprocessed using fMRIPrep. fMRIPrep preprocessing includes skull stripping using Advanced Normalization Tools (ANTs); susceptibility distortion correction using field maps; tissue segmentation using FSL's Automated Segmentation Tool (FAST); and spatial

normalization to Montreal Neurological Institute (MNI) 152-Asymmetrical space using ANTs' registration option. Functional data will be co-registered to anatomical data using FSL's FMRIB's Linear Image Registration Tool (FLIRT) with boundary-based registration. Functional data will additionally be motion corrected using FSL's MCFLIRT. In FSL, final preprocessing will include spatial smoothing using a 5mm full width half maximum isotropic Gaussian kernel, high-pass filtering, and adjusting for nuisance regressors, including the 6 motion parameters, the derivatives of each, and high motion time points (FD>0.9mm). A functional run for a subject will be excluded if >25% of total volumes are flagged as high motion points.

fMRI primary analyses: Neuroimaging analyses will be primarily completed in FSL (FMRIB Software Library, [www.fmrib.ox.ac.uk/fsl](http://www.fmrib.ox.ac.uk/fsl)). Within-run (level 1), within-subject (level 2) and group-level (level 3) analyses will be carried out in FSL's FMRIB Expert Analysis Tool (FEAT). At the 1st (within-run) level, models will assess brain response to the following contrasts of interest: effect of milkshake cue (milkshake cue > h2o cue) and effect of milkshake taste (milkshake taste > h2o taste). Inverse contrasts (h2o cue > milkshake cue; h2o taste > milkshake taste) will also be assessed.

At the 2nd level analyses, to test Aims 1 and 2, milkshake cue > h2o cue and milkshake taste > h2o taste contrasts will be carried forward to a fixed effects within-subject t-test estimating individual-level differences as a function of bromocriptine, i.e., active drug (bromocriptine) > placebo. Bilateral striatum will be used as the a priori region of interest (ROI). Binary masks of caudate, putamen and ventral striatum will be included in the level 2 within-subject models to extract parameter estimates for the contrasts of interest only within those regions. Extracted parameter estimates will be averaged across the three regions resulting in a single striatal parameter estimate value per contrast per subject.

For group-level analyses, striatal parameter estimates will be entered in 2x2 repeated measures mixed models including drug-by-gene interactions. As there are two scans, pre-scan covariates will likely vary between the two scans, as such pre-scan thirst and milkshake pleasantness ratings from both visits will be included as time-varying covariates. Models will also include visit order, BMI, and gender as covariates.

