# 2. Testing Visits - Outline

At the Neuropsychology of Ingestive Behavior Lab

Baseline: Fasting blood draw, fasting drug or placebo administration

Baseline-60 minutes: Visual analogues scales (VAS) hunger and satiety, height and weight measurement, demographic and psychological surveys, waiting for drug to become active 60 minutes: Walk to Biomedical Research Imaging Center

At the Biomedical Research Imaging Center

90 minutes - 150 minutes: VAS hunger and satiety, MRI assessment, taste administration, resting state, anatomical scans

At the Neuropsychology of Ingestive Behavior Lab

150 minutes-180 minutes: VAS hunger and satiety, fixed milkshake consumption

180 minutes: Blood draw

180 minutes-210 minutes: Behavioral impulsivity, surveys

210 minutes: Blood draw

210-240 minutes: VAS ratings, hedonic ratings, ad libitum food intake

The testing visit will last approximately 4 hours. Testing visit occurs twice for each participant.

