## 2. *Exploratory Outcomes*

Appetitive hormone analysis: Participants will have three blood draws per visit. For each visit, the first blood draw (fasting) will occur at the start of the visit prior to drug administration. Second blood draw will occur 180min after drug administration (and 30min after a fixed milkshake consumption). Third blood draw will occur 210min after drug administration (and 60min after a fixed milkshake consumption). Blood samples for satiety hormones will be assayed using Bio-Plex Pro Human Diabetes 7-plex Assay (Bio-rad, Hercules, CA). This kit analyzes adiponectin, amylin, and GLP-1. Additionally, a custom Human Cancer Panel 1 with only prolactin will be used to analyze prolactin concentrations (Bio-rad, Hercules, CA) using a Millipore Luminex (Darmstadt, Germany). Using the 3 timepoints for the blood draws, we will create the area under the curve (AUC) for each appetitive hormone (prolactin, adiponectin, amylin, GLP-1, insulin) for each visit. AUC values will be entered into 2x2 repeated measures mixed models including drug-by-gene interactions. Control variables of no interest to be included are BMI, gender, visit number, and baseline (fasting) hormone levels.

Behavioral response inhibition analysis: Reaction time, % commission errors and % omission errors from the Stop Signal Task will be used as a behavioral measure of inhibition. The three outcome variables will be entered into 2x2 repeated measures mixed models including drug-by-gene interactions. Control variables of no interest to be included are BMI, gender, visit number, and pre-task nausea ratings.

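### Hunger is analysed as a raw fasted-to-fed change without the fasted rating as a covariate, which generally costs some precision in the drug contrast

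*SAP*

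**What the plan says.** SAP section B.1 puts several behavioural measures into one type of model. For hunger the outcome is a difference: "changes in hunger (fasted to fed) will be entered into 2x2 repeated measures mixed models including drug-by-gene interactions". The covariates for these models follow: "Control variables of no interest to be included are BMI, gender, visit number and nausea (after scan assessments only". Fasted hunger is not listed.

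Elsewhere the SAP does use visit-specific baseline information. The hormone models in section B.2 state: "Control variables of no interest to be included are BMI, gender, visit number, and baseline (fasting) hormone levels". The striatal models in section B.1 take pre-scan thirst and pleasantness ratings from both visits as time-varying covariates.

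On timing, SAP B.2 says of the hormone baseline that "the first blood draw (fasting) will occur at the start of the visit prior to drug administration". Nothing equally explicit exists for hunger. The visit outline in Protocol section F.2 begins "Baseline: Fasting blood draw, fasting drug or placebo administration", and its next block reads "Baseline-60 minutes: Visual analogues scales (VAS) hunger and satiety, height and weight measurement, demographic and psychological surveys, waiting for drug to become active". Protocol section C mentions fasting-state hunger scales at each visit but does not fix their order relative to the dose. Further hunger ratings are listed at 90-150 minutes and in the block "150 minutes-180 minutes: VAS hunger and satiety, fixed milkshake consumption", and unspecified VAS ratings at 210-240 minutes. Neither document says which of these ratings are the fasted and the fed one.

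**The concern.** Subtracting the fasted rating assumes that a person who arrives 10 points hungrier at one visit than at the other will also be 10 points hungrier when fed. After a fixed 12 fl oz milkshake a partial carry-over is more plausible. If so, chance visit-to-visit variation in fasted hunger enters the drug-placebo comparison in full, when a covariate would remove the part that does not carry over. Such variation is to be expected, since the fast may last 6 to 8 hours and visits are two weeks apart.

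What is at stake is precision: wider intervals and lower power for the drug and drug-by-gene tests on hunger. The fasted rating is already collected, so nothing practical prevents its use.

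**Working it through.** **The plan's own figure.** The only stated calculation is 21 per group, 42 in total, for 0.8 power at r = .30 (SAP section A). That r is an effect size, not the correlation used below. Take f = 0.30/√(1 − 0.09) = 0.314, a 2-group by 2-measurement interaction test, two-sided alpha 0.05 and zero correlation between measurements. The noncentrality is then 0.314² × 42 × 2 ≈ 8.3 and the power is 0.803; 42 is the smallest even total that reaches 0.80. Alpha and the zero correlation are assumptions, because the SAP states neither. The figure is not specific to hunger and serves here only to set N = 42.

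**Set-up for hunger.** For each person take the drug-minus-placebo difference in the fasted rating and in the fed rating. Let r be their correlation and k the ratio of the fed SD to the fasted SD. Neither is in the documents. In units of the fasted variance:

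- raw change: 1 + k² − 2rk
- adjusted for the fasted rating: k²(1 − r²)
- raw minus adjusted: (1 − rk)²

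The last line is never negative and is zero only when rk = 1. With a fasted rating unaffected by drug, adjustment therefore cannot be less precise, apart from one or two degrees of freedom.

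**Equal variances (k = 1).** The adjusted/raw ratio reduces to (1 − r²)/(2(1 − r)) = (1 + r)/2. If the raw change has 80% power at two-sided 0.05, adjusted power is approximately Φ(2.80/√ratio − 1.96). The simulated ratios come from a 42-person crossover with order and gene in the model, 4,000 runs per case.

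| r | ratio by formula | ratio simulated | power if raw change has 80% |
|---|---|---|---|
| 0.3 | 0.65 | 0.66 | 93.5% |
| 0.5 | 0.75 | 0.77 | 90% |
| 0.7 | 0.85 | 0.87 | 86% |
| 0.9 | 0.95 | 0.98 | 82% |

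At r = 0.5, an adjusted analysis would match the precision of 42 people under raw change with 42 × 0.75 = 31.5.

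**Unequal variances.** With k = 1.4 the ratio is:

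- r = 0.3: 1.96 × 0.91 / (2.96 − 0.84) = 0.84
- r = 0.5: 1.96 × 0.75 / (2.96 − 1.40) = 0.94
- r = 0.7: 1.96 × 0.51 / (2.96 − 1.96) = 1.00, no gain

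With k below 1 the gain is larger: at k = 0.7 and r = 0.5 the ratio is 0.49 × 0.75 / (1.49 − 0.70) = 0.47.

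**If the fasted rating is post-dose.** Suppose the true drug effect on fed hunger is −0.50 SD, the drug has already moved the fasted rating by −0.20 SD, r = 0.5 and k = 1. Raw change estimates −0.50 + 0.20 = −0.30. The adjusted model estimates −0.50 + 0.5 × 0.20 = −0.40. Simulation gave the same values. Neither recovers the full effect on fed hunger, but the adjusted model comes closer.

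**The case against.** The strongest objection concerns the baseline itself. By the Protocol F.2 outline, dosing comes at time 0 and the earliest hunger rating falls in the block after it. Protocol C puts drug activity at about 60 minutes and Protocol G schedules the scan at about 90 minutes to allow maximum plasma concentration, so exposure may already be rising when that rating is taken. Adjusting for a post-dose rating is more than a precision step, because it changes what the drug effect means. This stands as a reason to settle the timing and state the interpretation. It does not defend the current plan: an early drug effect enters the raw change in full and the adjusted estimate only in part.

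A reader might infer from the hormone models that the SAP contradicts itself and gives up precision on hunger for no reason. The documents do not support that. The hormone outcome is an AUC with no subtraction of the fasting level described, and its baseline is explicitly pre-dose. The hunger outcome already handles baseline, by subtraction. These are two methods of handling baseline, and the SAP simply gives no reason for its choice.

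A reader might also take the equal-variance figures as a guaranteed gain, say at least 5 points of power for any r up to 0.7. That does not hold either. A separate simulation with 21 per order and 8,000 runs gave 0.85 against 0.81 at r = 0.7, a gain of 4 points, and at k = 1.4 and r = 0.7 the gain is nil.

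The stakes are also limited. Treatment is blinded, order is counterbalanced and visit number is in the model. Aim 1 names BOLD response, hedonic ratings and ad lib intake, not hunger change. The sample size rests on the TaqIA comparison.

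**Conclusion.** The point holds as a low-severity precision improvement on one listed outcome. Leaving out the fasted rating generally makes the drug contrast on hunger less precise. The variance reduction from including it is 35% at r = 0.3, 25% at 0.5, 15% at 0.7 and 5% at 0.9 under equal variances, and it falls to nothing when rk is near 1. These figures rest on assumed values of r and k, on a fasted rating unaffected by drug, and, for power, on two-sided alpha 0.05.

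A reader might infer that the planned hunger result is biased or that the trial's main conclusions are weakened. Neither follows. With a fasted rating unaffected by drug, the raw change estimates the drug effect without bias from this source, and no main conclusion depends on this model.

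**What to change.** In SAP section B.1:

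1. Name the VAS ratings that count as fasted and fed for the change in hunger, by their place in the visit outline, with the earliest rating of the visit as the fasted one.
2. Add the same-visit fasted hunger rating to the hunger model as two terms: the person's mean over the two visits, and the visit's deviation from that mean. A single slope would mix between-person and within-person relations; only the within-person part adjusts the drug contrast. The outcome can stay as the change, because with these terms included, change and fed rating give the same drug estimate.
3. Reconcile Protocol sections C and F.2 on whether the fasted rating precedes dosing. If it is post-dose, state that the adjusted drug effect is conditional on that early rating.

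The cost is two model terms, about one degree of freedom in the within-person contrast, a few lines of text and no new data. The change should be made before analysis.

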#### B. Study Objectives

**Aim 1**: To test the hypothesis that acute bromocriptine administration will alter neural and perceptual hedonic drivers of eating behavior (Visual analog scales), both contributing to a decrease in palatable food intake in those at high risk for T2DM. We expect that bromocriptine will increase BOLD response during palatable food intake in dopaminergic brain regions thought to encode reward and increase perceptual hedonic food ratings. We also expect that bromocriptine will result in decreased ad lib palatable food intake.

**Aim 2**: Test whether the A1 variant of the DRD2 TaqIA polymorphism, which is associated with reduced dopamine-D2 receptor density and dopamine signaling, moderates the impact of bromocriptine on neural and perceptual hedonic drivers of eating behavior. By testing the bromocriptine by TaqIA allele status interaction, we expect that the effects described in aim 1 will be pronounced in those with at least 1 A1 variant of the TaqIA polymorphism.

Exploratory Aim 1: To test the hypothesis that acute bromocriptine administration will alter the homeostatic mechanisms of satiation (meal termination). We expect bromocriptine to modify endocrine-mediated satiation signaling via suppressed prolactin, augmented adiponectin, amylin, glucagon like peptide-1 (GLP1), and decrease postprandial plasma glucose and insulin.

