# C. Study Design

This within-subject pilot study will look at 180 overweight/obese (25 < BMI < 35) adults ages 18-35 years of age. All participants will be screened at the first visit for 50 eligible participants who will complete the other visits. 25 participants will have the DRD2 TaqIA A1 allele and 25 will have the A2/A2 variant. The study will be completed over two testing visits with a two-week washout period in between. Following published reports of the effect of acute administration of bromocriptine (10), participants will be given a 1.6mg dose of either bromocriptine-QR (Cycloset) or a placebo after a 6-8 hour fast, paralleling the recommended dosage and time of administration (11). Order of agonist/placebo will be counterbalanced across the two visits. At both visits, the participant will have a fasting blood draw, anthropometric measurements, complete visual analogue scales (VAS) for hunger, and satiety and surveys. Once bromocriptine/placebo is metabolically active (~60 mins) subjects will undergo a functional MRI with our milkshake receipt paradigm and a resting state MRI to assess functional connectivity. The Biomedical Research Imaging Center (BRIC) is located on the UNC-CH campus and 7-10 min walk from our laboratory (Neuropsychology of Ingestive Behavior Laboratory). Post-MRI, subjects will consume a fixed portion of milkshake (12 fl oz) and perform VAS hedonic ratings; will complete a test of reaction time and behavioral impulsivity, and two postprandial blood draws (30 & 60mins post milkshake ingestion). Finally, subjects will perform perceptual hedonic assessments of palatable foods and given the opportunity for ad lib consumption.

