#### I. Study Intervention Administration

This is a within subjects designed experiment, so all subjects will receive the Cycloset and placebo. The administration will be blinded to subject and the research. [name] will oversee the blinding procedure. The order of the drug and placebo will be counterbalanced across the two visits, and [name] will see to the drug/placebo administration schedule. Because the screening visit is before the testing visit and randomization we are confident in the participant's eligibility.

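### The BMI and gender covariates cannot change the drug-by-genotype test of Aim 2; a drug response that differs by sex or BMI would be credited to TaqIA if the genotype groups also differ in sex or BMI

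*SAP*

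**What the plan says.** Protocol section I describes a crossover: "This is a within subjects designed experiment, so all subjects will receive the Cycloset and placebo". Section B defines Aim 2 through an interaction: "By testing the bromocriptine by TaqIA allele status interaction, we expect that the effects described in aim 1 will be pronounced". Section C sets the genotype groups by selection: "25 participants will have the DRD2 TaqIA A1 allele and 25 will have the A2/A2 variant". Neither document states matching on BMI or gender.

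SAP B.1 (behavioural data) says that the outcomes "will be entered into 2x2 repeated measures mixed models including drug-by-gene interactions which addresses Aim 1a and Aim 2". It then lists the covariates: "Control variables of no interest to be included are BMI, gender, visit number and nausea (after scan assessments only"). An interaction with p<0.10 is followed by four contrasts: genotype effect on drug (1), genotype effect off drug (2), drug effect in A2/A2 (3) and drug effect in A1 carriers (4).

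The fMRI group model has the same structure: "Models will also include visit order, BMI, and gender as covariates". So do the hormone models in B.2, "Control variables of no interest to be included are BMI, gender, visit number, and baseline (fasting) hormone levels", and the stop-signal models. Drug-by-gene is the only interaction named anywhere. The SAP does not use the term main effects for BMI and gender, but that is the plain reading of these lists.

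**The concern.** Drug order is assigned by the trial, but genotype is not, so A1 carriers and A2/A2 participants may differ in sex or BMI. A reader who sees BMI and gender among the control variables will assume that the Aim 2 test is protected against such differences. In a crossover that protection does not come from these terms.

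If women, or heavier participants, respond differently to bromocriptine and are more common in one genotype group, the difference appears as moderation by TaqIA, or masks real moderation. The Protocol's rationale is a genetically informed, personalised treatment, so this is the inference that matters most. The p<0.10 threshold for follow-up contrasts makes a spurious signal somewhat easier to pursue.

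**Working it through.** **1. Algebra.** For person i, let G be genotype and S a person-constant covariate (gender, or BMI over two weeks). In the planned model, S adds the same amount at both visits, so

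drug minus placebo = drug effect + (drug-by-gene) × G + visit effect + error.

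S is absent. If the drug effect also changes by δ per unit of S, and no drug-by-S term is fitted, then

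expected drug-by-gene estimate = true value + δ × (mean of S in A1 carriers − mean of S in A2/A2).

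The bias is imbalance × difference in drug effect. It is zero if either factor is zero.

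**2. Numerical check** (simulated crossover, random-intercept model).
- One dataset, 21 per genotype, complete pairs: the interaction is −0.160674 (SE 0.300618) without BMI and gender, and identical with both as main effects. With drug-by-covariate terms it is −0.473 (SE 0.309).
- The genotype difference at placebo (contrast 2) does respond to the main effects, moving from 1.44 to 1.00.
- Repeated datasets with true interaction 0, a 1 SD BMI difference between genotypes and a BMI-by-drug slope of 0.5 (both assumed):

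| Situation | Mean, no covariates | Mean, main effects | Mean, drug-by-covariate terms |
|---|---|---|---|
| Complete pairs | 0.474 | 0.474 | −0.018 |
| 8 of 50 missing one visit | 0.508 | 0.508 | −0.004 |
| Time-varying nausea in model | 0.499 | 0.498 | 0.020 |
| BMI re-measured at each visit | 0.533 | 0.534 | 0.013 |

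In the last three rows individual estimates shift by 0.02 to 0.03 on average, but the bias does not fall.

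**3. Size for sex.** Assumptions: drug effect differs by 0.6 outcome units between the sexes; SD of change 1.15; 25 per group; no true gene effect. The interaction SE is about 1.15 × √(2/25) = 0.325.
- 20-point imbalance (15 v 10 women of 25): 0.20 × 0.6 = 0.12, or 0.12/0.325 = 0.37 SE. Error rates stay near nominal.
- 48-point imbalance (19 v 7 women of 25): 0.48 × 0.6 = 0.288, or 0.89 SE. In simulation p<0.10 occurs in about 21% of trials, against about 11% with drug-by-covariate terms; p<0.05 in about 12% against about 6%.
- If sex is independent of genotype with 50% women (assumed), chance gives a gap of at least 20 points with probability 0.203, and of at least 48 points with probability about 0.0009.

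**4. Size for BMI.** Assumed differences of 0.25 to 1 SD and slopes of 0.2 to 0.5 per SD give biases from 0.25 × 0.2 = 0.05 to 1 × 0.5 = 0.50.

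**5. Cost in precision.** At 48 points, sex explains about 0.48² = 0.23 of genotype variance, so the SE rises by up to √(1/(1−0.23)) = 1.14. Simulation gives about 12% once the gain in residual fit is counted. At 20 points the factor is √(1/0.96) = 1.02, and simulation gives roughly 0-3%.

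**6. Cost in power.** The SAP's N of 42 can be reproduced: r = .30 gives f = 0.30/√(1−0.09) = 0.3145; for a 2 × 2 within-between interaction λ = 0.3145² × 42 × 2 = 8.31 on 40 df, power 0.803. This needs two-sided alpha 0.05 and zero within-person correlation, neither of which is stated. On the same basis, after adding two terms:

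| Genotype variance explained by BMI and gender | Power, N=42 | Power, N=50 |
|---|---|---|
| 0% | 0.802 | 0.868 |
| 10% | 0.760 | 0.832 |
| 20% | 0.710 | 0.786 |

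**The case against.** The strongest reply is that the crossover already does the work: each person is their own control, so no additive BMI or gender effect can enter the interaction. That stands. A reader might infer that Aim 2 is wholly uncontrolled for BMI and gender. The documents do not support this, since only differential drug response remains open.

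Second, no bias is demonstrated. The documents report neither a drug-by-sex or drug-by-BMI effect nor any association of TaqIA with sex or BMI. Chance imbalance alone does not distort the test: with sex independent of genotype and a 0.6 drug-by-sex effect, simulation gives a mean estimate near 0 and about 5% rejection at the 0.05 level, with or without the extra terms. That also stands. It would be too strong to say that the trial is likely to report false genetic moderation.

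Third, the covariates are not useless. Contrasts 1 and 2 compare different people and are adjusted by them. Contrasts 3 and 4 are within-person drug effects, each valid for its own group; only attributing their difference to the allele is in question. Aim 1's pooled drug effect is not confounded.

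Fourth, the extra terms cost most precision where imbalance is largest, and the Protocol calls this a pilot. That argues against insisting that they replace the planned model. It does not argue against pre-specifying them beside it.

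**Conclusion.** The point holds in a limited form. As listed, BMI and gender cannot remove bias from the Aim 2 interaction or from the comparison of contrasts 3 and 4. With complete pairs the estimate is exactly unchanged; with missing visits or time-varying covariates it moves slightly and the bias remains.

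Whether bias arises depends on two quantities that the documents do not give: how far drug response differs by sex or BMI, and how far the genotype groups differ on that factor. On the assumed 0.6 sex difference in drug effect, the consequence is small at a 20-point imbalance (0.12) and material only at an extreme one (0.29 at 48 points). If sex and BMI are unrelated to genotype, the test keeps its nominal error rate. This is an inexpensive safeguard for the conclusion on genetic moderation, not a flaw that invalidates the design.

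**What to change.** For every model used for Aim 2 (behavioural, striatal, hormone, stop-signal):
- Pre-specify a version that adds drug-by-gender and drug-by-BMI, with both covariates mean-centred, to the planned terms. Report the drug-by-gene estimate and contrasts 3 and 4 from it beside the planned model, at least as a sensitivity analysis.
- Tabulate BMI and gender by genotype group.
- Do not describe the drug-by-gene result as adjusted for BMI and gender on the strength of the main effects alone.

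The cost is SAP wording and two model terms per outcome, using data already collected. In precision it is 2 degrees of freedom plus the SE increase worked out above, which is small unless the groups are badly imbalanced. Keeping the planned model as primary leaves its power untouched.

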## **Statistical Analysis Plan**

### **A. Sample Size and Power**

We will recruit and screen 180, 18-35 year old overweight/obese individuals in order to enroll 50 participants with and without the presence of the DRD2 TaqIA A1 allele, and at high risk for T2DM by virtue of HbA1c. The n=42 represents the number of participants who will provide usable data and accounts for possible attrition and negative side effects of the bromocriptine (based on previous repeated measures fMRI studies and reports of bromocriptine, expected attrition is 4%-7%). In evaluating our inclusion/exclusion criteria (see below) conservatively we anticipate 180 participants per year will be eligible for the present investigation. Of those, based on previous work, 36 are expected to have one A1 variant of the TaqIA polymorphism and 144 to have A2/A2 (per each recruitment year). Therefore, over the three-year duration of the present study, we will have ample opportunity to meet our recruitment targets (Y1: n= 17; Y2: n= 18; Y3: n= 15). Power analyses were conducted using fMRIPower (for fMRI contrasts described in Aim 1b) and G\*Power (for lab measures) to determine sample size based on previous work (25). Sample sizes were determined by the between-group (TaqIA allele status; Aim 2) difference, which is the least sensitive of the proposed tests. Based on a small to medium sized effect ( $r = .30$ ), we determined that a similarly sized strategy-by-assignment interaction would be detectable with 0.8 power with at least n=21 per group, yielding a total sample size of 42. To account for the small possibility of complications with blood draws, excessive movement in the scanner, side effects from the medication or other protocol deviations we plan on recruiting a total of 50 (25 per cell).

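### After-scan outcomes are modelled only with post-dose nausea as a covariate, so no planned model gives the total drug effect on intake; the fMRI group model shares this only if its pre-scan ratings are taken once the drug could have acted

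*SAP*

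**What the plan says.** **Behavioural outcomes.** SAP B.1 models as outcomes "VAS scales for milkshake, snack food pleasure and desire, ad lib intake of those foods", together with the fasted-to-fed change in hunger, in 2x2 mixed models with drug-by-gene interactions. The covariates are fixed in one sentence: "Control variables of no interest to be included are BMI, gender, visit number and nausea (after scan assessments only". SAP B.2 handles the stop-signal outcomes in the same way, with nausea rated before the task.

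**fMRI outcome.** In the group-level model for the striatal estimates, "pre-scan thirst and milkshake pleasantness ratings from both visits will be included as time-varying covariates". The reason given is "As there are two scans, pre-scan covariates will likely vary between the two scans". Visit order, BMI and gender are also included. The only drug contrast without these ratings comes one level down, as a "fixed effects within-subject t-test estimating individual-level differences as a function of bromocriptine".

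**Hypotheses.** Protocol B, Aim 1 expects bromocriptine to "increase BOLD response during palatable food intake in dopaminergic brain regions thought to encode reward and increase perceptual hedonic food ratings" and to reduce ad lib intake of palatable food.

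**Timing.** Protocol F.2 places dosing at Baseline, before any VAS that it lists, with the scan block at 90 to 150 minutes and the behavioural outcomes after it. Protocol C and F.2 treat the drug as becoming active at about 60 minutes. For the hormone models, SAP B.2 does time its covariate: "the first blood draw (fasting) will occur at the start of the visit prior to drug administration".

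**Nausea.** Protocol H lists nausea among the drug's adverse effects and describes it as the one reported most often.

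**The concern.** Each person has one visit on drug and one on placebo. A covariate that differs between the visits may therefore differ because of the drug, and adjusting for it takes out whatever part of the drug effect runs through it. Nausea is the clear candidate: it is a recognised effect of the drug, it is rated after dosing, and it can plausibly change how much people eat and how they rate food.

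Aim 1 says that the drug will reduce intake, without restricting this to a reduction not caused by nausea. The SAP neither narrows that target nor plans a model without nausea. If intake falls in the adjusted model, the reader cannot tell how large the whole fall was. If it does not fall, the reader cannot tell whether nausea absorbed the effect.

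The pre-scan ratings in the fMRI model raise the same question, subject to timing. Protocol G (ad lib taste test) counts pleasantness among the hedonic ratings, and SAP B.1 analyses milkshake VAS as an outcome of drug. The same kind of rating is thus an outcome in one model and a covariate in another.

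**Working it through.** **1. The plan's own figure.** The SAP says that a "similarly sized strategy-by-assignment interaction would be detectable with 0.8 power with at least n=21 per group", based on r = .30. With f = 0.30/sqrt(1 - 0.09) = 0.314, within-person correlation 0 and two-sided alpha 0.05 (the last two are my assumptions), the noncentrality is 0.0989 x 42 x 2 = 8.31 and power is 0.803. So 42 can be reproduced, and nothing here changes it. That 0.8 belongs to the interaction; the SAP states no power for the drug main effect.

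**2. Timing of each covariate.**
- Nausea, after-scan outcomes: these outcomes fall at or after about 150 minutes, well past the stated 60 minutes to activity. The outline lists no VAS before dosing.
- Nausea, stop-signal task: the task is at 180 to 210 minutes.
- Pre-scan thirst: thirst is a named VAS item (Protocol G) but has no stated time.
- Pre-scan milkshake pleasantness: not among the VAS items in Protocol G and not in the outline before the scan. The milkshake hedonic rating that Protocol C does schedule is after the MRI.
- Fasting hormone level: stated to be before the dose.

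**3. Formula.** Let a be the drug's shift in the covariate and b the covariate-outcome slope, both in visit-level SD units. With no unmeasured common cause of covariate and outcome:

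adjusted drug effect = total effect - a x b

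**4. Numbers.** The documents give neither a nor b, so these figures only illustrate the mechanism. Assumed: total effect 0.45 visit SD, 42 people (21 per TaqIA group), two visits, intraclass correlation 0.5 for outcome and covariate. Power is from simulation (20,000 replicates per setting, random-intercept REML model with drug, TaqIA, their interaction, visit and order; BMI and gender omitted; two-sided 0.05). Without the covariate the estimate is 0.45 and power is 0.81 to 0.82. With it:

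| a | b | 0.45 - a x b | Power |
|---|---|---|---|
| 0 | 0.3 | 0.45 | 0.85 |
| 0 | 0.5 | 0.45 | 0.90 |
| 0.2 | 0.2 | 0.41 | 0.74 |
| 0.3 | 0.3 | 0.36 | 0.64 |
| 0.5 | 0.3 | 0.30 | 0.46 |
| 0.5 | 0.5 | 0.20 | 0.27 |
| 0.3 | -0.3 | 0.54 | 0.93 |
| 0.5 | -0.3 | 0.60 | 0.96 |

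**5. Direction.** The outcome is signed so that the hypothesised effect is positive. For intake, where a fall is expected, nausea that lowers intake gives a positive b, and the adjusted effect shrinks: 0.45 - 0.3 x 0.3 = 0.36, a loss of 0.09/0.45 = 20%. For hedonic ratings, where a rise is expected, nausea that lowers ratings gives a negative b, and the adjusted effect grows: 0.45 + 0.5 x 0.3 = 0.60.

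**6. Centring.** The SAP does not say that these covariates are centred within person, so the fitted slope mixes within- and between-person association. With a within-person slope of 0, the estimate still falls to 0.42 (shift 0.3, between-person slope 0.3) or 0.36 (0.5 and 0.5).

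**7. Aim 2.** The drug-by-TaqIA coefficient changes only if the drug moves the covariate differently by genotype. I give no figure for it. The share removed depends on how r = .30 is turned into a contrast, and the SAP does not state the within-person correlation needed to settle that.

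**The case against.** **An effect not through nausea is a fair target.** This stands. Aim 1 concerns hedonic drivers of eating, and a fall in intake caused only by feeling sick would not support it. A reader might infer that adjusting for nausea is an error; the documents do not support that. What is missing is a statement of the target and a companion model. The adjusted coefficient also has that meaning only if nausea and the outcome share no unmeasured visit-level cause.

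**The drug may not move nausea here.** This is possible. Then nothing is biased and adjustment gains precision, but only results from both models would show it.

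**The fMRI ratings may precede drug action.** This also stands. A reader might infer that the fMRI model certainly removes part of the drug effect on striatal response. No section times the pleasantness or thirst rating. Even a rating made after the dose could fall in the first hour, when the protocol itself describes participants as waiting for the drug to become active. Nor does any section say that the drug changes thirst.

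**The level 2 contrast already omits the ratings.** It does, but it is an individual-level step. The only group-level model stated includes them.

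**The magnitudes are assumed.** They are. The power losses are not losses against anything the SAP planned, since its 0.8 is for the interaction.

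**Conclusion.** The point holds firmly for nausea and conditionally for the fMRI model. For the after-scan behavioural outcomes and the exploratory stop-signal outcomes, the only planned model conditions on a post-dose rating of a known drug effect. If the drug raises nausea and nausea is associated with the outcome, the reported coefficient is not the total effect, and no planned analysis shows by how much it differs.

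Size and direction cannot be known from the documents. The illustrations run from 0.20 to 0.60 against an assumed total of 0.45, with no change if the drug does not shift the covariate. A reader might infer a bias toward no effect throughout; the sign depends on the outcome, and hedonic ratings could go the other way.

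For fMRI, the certain defect is that the timing of pleasantness and thirst is not stated. Whether the model departs from the total effect depends on that timing and on whether the drug moves these ratings. The documents do not require the total effect to be primary for either set of outcomes; they need to say which effect is. This should be fixed before analysis, but it does not invalidate the design.

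**What to change.** 1. For each after-scan outcome in SAP B.1 and each stop-signal outcome in SAP B.2, pre-specify and report a model without nausea (total effect) beside the nausea-adjusted model (effect not through nausea). Declare in advance which is primary.
2. State when pre-scan pleasantness and thirst are rated relative to dosing. If the drug could already have acted, add a group-level fMRI model with only drug, TaqIA, drug-by-TaqIA, visit order, BMI and gender. Report it beside the adjusted model and declare in advance which is primary. If the ratings are made before the dose, say so and keep the model as it is.

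The cost is SAP wording and one extra model per outcome, with no new procedure or data. If the drug does not move the covariate, the model without it is less precise: power of about 0.81 instead of 0.85 at an assumed slope of 0.3, or 0.81 instead of 0.90 at 0.5. The second gap is not trivial at 42 people, but the adjusted result is still reported. A fall in intake without adjustment must be read together with the nausea-adjusted result.
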